### Sampling Duration, Time Frame, and work plan:

Background /Pilot Study	Survey	Observation Period (1 st Data Set/Phase 1 )	Washo ut	Survey	Observation Period (2 nd Data Set/ Phase 2)	Wash out	Survey	Observation Period (3 rd Data Set/ Phase 3)
8 weeks	4 weeks	4 weeks	3 week	2 Week	4 weeks	3 week	2 week	4 weeks
04 Sep -30 Oct (2017)	31 Oct – 28 Nov (2017)	01 Dec - 30 Dec (2017)	1st Jan - 05 Feb (2018)		06 Feb – 08 Mar (2018)	26 Mar – 30 Apr (2018)		22 May – 20 Jun (2018)
		8 curtains from Male  12 curtains from Female Cubicle  50% coated curtain, 50% standard curtain			12 Curtains from Male Cubicles  12 Curtains from Female Cubicle  50% coated curtain, 50% standard curtain			16 Curtains from Male Cubicles  16 Curtains from Female Cubicle  50% coated curtain, 50% standard curtain
		No of samples: 480			No of samples: 576			No of samples: 768

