half of the curtains as control in the same setting in a cubicle. As the study was double blind, so coding was done to identify the treatment as control curtains.

[5] Sample were taken from eight highly touched areas of 50x50 cm^2 on weekly bases for three consecutive weeks on 7th day of first installation. On each period/phase 480, 576 and 786 samples were collected accordingly using the developed sample protocol. In total, the investigators collected 1824 samples from 76 patient privacy curtains in which 912 (50%) were control curtain and 912 (50%) are antimicrobial coated curtains.

[6] Healthcare workers from the participating wards were assessed for their acceptance of the multilevel antimicrobial disinfectant coating by way of a questionnaire. Additional reformulation may be necessary to increase the acceptability of the coating technology to the healthcare workers.

[7] For the bacteria count, duplicate plates of TSA (total bacteria count) and Chromagar MRSA (selective agar for MRSA detection) were used for enumeration. CFU/m^2 is calculated after 48 hours' incubation at 37C. Data was analyzed using SPSS V.21 to assess the effectiveness of the coating in reducing the contamination level of the surface. The total bacteria count on the patient privacy curtains was compared between the control and treatment group using Mann-Whitney test and T-test. ANOVA analysis allowed the comparison of different periods of study of phase wise as well as week wise. The significance of the statistical test is defined to have a P value <0.05.

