## **Study Objectives**

1) To compare the antibacterial effect of in use antimicrobial coated patient privacy curtains with standard curtains:

- i) Total bacterial count over time
- ii) Time of first MDRO contamination
- iii) Percentage of MDRO contamination

2) To assess healthcare worker's acceptance of the multi-level antimicrobial coating.

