## **Primary Outcome Measure:**

1. Change in total bacteria count and MRSA in control vs treatment patient privacy curtains

To quantify the effectiveness of antimicrobial coating, percentage change (both in log and linear scale) in mean bacterial count (CFU/m^2 units) in control versus treatment curtains is used. The data was collected in 3 phases of 4 weeks each, so the time frame used is representative of the complete observation period.

[Time Frame: 12 weeks]

2. Durability of antimicrobial coating in affecting bacterial load amongst treated patient privacy curtains

Change in bacterial load amongst treatment curtains is observed as a function of time during each phase of the data collection period (for 4 weeks). In total, data was collected in 3 phases of 4 weeks each, so the total observation period is 12 weeks and timeframe of each frame is 4 weeks.

3) [Time Frame: 12 weeks]

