## 2. Curtain installation:

1. Every 3rd week, our team changed the curtains from 2 cubicles (1 male and one female) according to curtain changing policy of hospital.
2. At the start of every phase of study, following the standard protocol; after taking official consent from ward manager we changed the curtains at once from both cubicles.
3. There were two types of curtains clippings, with metal ring and cloth strips so that curtains were changed according to the type of clips/ring.
4. As there was the capacity of 12 curtains in one cubicle, so six curtains were coated and six uncoated. The sequence was alternative as one coated next uncoated and so on. After installation, we informed ward manager about completion of curtain hanging in the designated ward and took first sample at day 7 because we gave sufficient time to curtains to be contaminate in hospital environment.
5. There was a backup pair of the curtain in case of need to change curtain due to spoilage, vomitus, blood or MDRO diagnosed the patient. Staff was informed to notify our team about the date and reason of curtain changing.

[figure not shown]

Fig 2. Illustration of curtains installation in cubicles as one control other treatment showing matched paired randomization

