### **Data Analysis:**

The duplicate system in total bacteria count helped to monitor the validity of the data point. Logical elimination of plate count was determined while comparing the bacteria morphology of the first plate with the second plate. If the bacteria morphology was not consistent, the plate with more bacteria was eliminated, and the plate with a lower value was taken due to the chance of contamination on a non-selective agar plate.

The Colony Forming Unit (CFU) obtained on the duplicated plates was averaged, and the CFU per unit area was calculated. CFU per unit area was allowing the comparison of microbiological contamination of the sampled surface. With the dilution factor of the samples, the Total bacteria count (TBC) was determined. The microbiological contamination level of an item was represented by the CFU/unit area of the item.

CFU on Müller-Hinton Agar represents the total aerobic bacteria count. By dividing the CFU with the area sampled, CFU/m^2 was obtained. Data points that did not contain any CFU count were assumed to have 0.5 CFU. The assumption was made based on the minimum detection value that can be obtained.

All analysis was carried out using Statistical Package for the Social Sciences for Windows, version 25.0 (SPSS, Inc., Chicago, IL, USA) to analyze the effectiveness of the coating in reducing the contamination level of the surface. The total bacteria count on the patient partition curtains was compared to the control and treatment group using Mann-Whitney test and T-test. Chi-square test and Fisher's exact test were also used to compare categorical variables such as the percentage of MRSA. Parametric test was carried out to evaluate the cleanliness baseline in each of the wards before and after treatment. ANOVA analysis allowed the comparison of different periods of study and the differences among wards. Median time to first contamination (days) of MDRO for each curtain type was compared using the Wilcoxon rank-sum test. The significance of the statistical test was defined to have a P value <0.05.

Healthcare workers from the participating wards were assessed for their acceptance of the multilevel antimicrobial disinfectant coating by way of a questionnaire. Additional reformulation may be necessary to increase the acceptability of the coating technology to the healthcare workers.

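### Primary outcome 2 judges coating durability from treated curtains alone, so drift shared with the control curtains is mixed with loss of coating effect

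*Combined protocol and SAP*

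**What the plan says.** Primary Outcome Measure, item 2, names durability of the coating and then defines the measure: "Change in bacterial load amongst treatment curtains is observed as a function of time during each phase of the data collection period". Item 1 of the same section does use a control-versus-treatment comparison, over the complete observation period.

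Study Objectives, objective 1, sets the aim "To compare the antibacterial effect of in use antimicrobial coated patient privacy curtains with standard curtains" and lists total count over time as its first component.

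Two places describe the analysis over time. Detailed Description [7] states "ANOVA analysis allowed the comparison of different periods of study of phase wise as well as week wise". Data Analysis states "ANOVA analysis allowed the comparison of different periods of study and the differences among wards" and does not mention weeks. Both name Mann-Whitney and t-tests between the arms, without a time term.

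Controls were available throughout. The work plan gives "50% coated curtain, 50% standard curtain" in each phase. Curtain installation, item 4, adds "The sequence was alternative as one coated next uncoated and so on". Under Environmental Sampling, item 1, every curtain is sampled three times at weekly intervals after a first week of exposure.

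**The concern.** Durability means that the difference between coated and uncoated curtains persists. The outcome measures something else: how the load on coated curtains moves. As a description of that load it is correct. The error comes when it is read as durability. Build-up on all curtains then looks like a fading coating, and a fall on all curtains can hide real fading.

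Shared drift is plausible here. Laundered curtains are hung clean, and the team "took first sample at day 7 because we gave sufficient time to curtains to be contaminate in hospital environment". That sentence covers only the first week. Continued drift between the first and third samples is an inference, and the documents neither state it nor rule it out.

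At stake is the conclusion from one of two listed primary outcomes. Outcome 1 is not affected.

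**Working it through.** **The plan's own figure.** The sample size section gives 542 per group, 1084 in total (one-sided 0.05, d = 0.2, power 0.95). Check: δ = 0.2 × √(542/2) = 3.2924, critical t = 1.6463 on 1082 df, power 0.9501. This reproduces. It covers the two-arm difference in means; no figure is given for durability.

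**Identity.** Let D be the drift shared by both arms and L the loss of coating effect, in log10 units between two samples.
- Treated change = D + L
- Control change = D
- Treated minus control = L

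With D = +0.2 and L = 0, the treated-only change is +0.2 and the contrast is 0. With D = −0.2 and L = 0.21 (the whole effect assumed in the sample size section), the treated-only change is +0.01 and the contrast is 0.21.

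**Inputs for the size.**
- From the documents: SD 1 log; 8 areas per curtain; 3 weekly samples; 20, 24 and 32 curtains per phase, half of them treated, so 10 + 12 + 16 = 38 treated.
- Assumed: drift of 0.05, 0.10 or 0.15 log per week. Shares of total variance (curtain / curtain-by-visit) of 0.1/0, 0/0.1, 0.1/0.1, 0/0.2 and 0/0.3, with the rest at area level.
- Test: a two-sided 5% t-test on curtain slopes. This is a stand-in, because the plan names no test for this outcome.

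**Formula.** Curtain slope = (third weekly mean − first weekly mean)/2, with variance 0.5 × (visit share + residual share/8). Two ends of the range, pooled, at +0.10:
- Shares 0/0.3: variance 0.5 × (0.3 + 0.7/8) = 0.19375; SE = √(0.19375/38) = 0.0714; noncentrality 0.10/0.0714 = 1.40; rejection 28%.
- Shares 0.1/0: variance 0.5 × (0.9/8) = 0.05625; SE = √(0.05625/38) = 0.0385; noncentrality 2.60; rejection 72%.

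**Treated-only test, intact coating** (noncentral t):

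| Shared drift, log/week | Within one phase | At least one of three phases | Pooled, 38 curtains |
|---|---|---|---|
| 0.05 | 6-12% | 19-29% | 10-24% |
| 0.10 | 10-35% | 31-63% | 28-72% |
| 0.15 | 16-66% | 49-91% | 53-97% |

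The pooled column takes the same drift in every phase. With no drift, three looks at 5% reject at least once in 1 − 0.95³ = 14%. In 20,000 simulated trials per scenario under shared drift, the coated-versus-control contrast rejects in 4.7-5.3% per phase and 4.7-5.1% pooled.

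**Precision of the contrast.** With equal arms its SE is √2 ≈ 1.4 times that of the treated-only slope: 0.054-0.101 pooled. The 95% CI half-width is 0.11-0.20 log/week pooled and 0.17-0.41 per phase. Power for a loss of 0.15 log/week is 31-78% pooled and 11-41% per phase. Losing the whole 0.21 log over two weeks is 0.105 log/week; pooled power for that is 18-48%.

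**Other SD.** The previous study's SDs were 0.53-0.54. At 0.54, the pooled treated-only test at +0.10 rejects in 71% to nearly 100%, and pooled contrast power for 0.105 log/week is 48-94%.

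**The case against.** The strongest reply is that outcome 2 is by its own title a within-arm measure, with no test or decision rule attached. Objective 1(i) fits the controlled outcome 1 at least as well, and the week-wise ANOVA may include arm. On this view only the word durability goes too far, and the rejection rates belong to a test the plan never names. This stands in part: the rates illustrate the size of the problem and are not error rates of the plan. It does not remove the point. The outcome is listed as primary and named durability, and no stated analysis gives an arm-by-week contrast. Main effects of arm and week would not answer the question either.

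A second reply is that the size depends on assumptions. That is true of drift and correlation, and the ranges are wide. A smaller SD makes the false signal from the treated-only trend stronger and the contrast more precise, so the direction does not change.

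A third reply has real force: the contrast does not identify durability without a further assumption. The coating is described as contact-killing and anti-adhesive, so it could slow build-up itself. Suppose coated curtains with an intact coating rise 0.15 and controls 0.05 log/week. The contrast is then significant in 17-44% of trials pooled and 8-21% per phase. No sample before day 7 is described, so equal drift cannot be checked. This limits how firmly the contrast may be read; it does not make the treated-only trend better.

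**Conclusion.** The concern holds. As defined, primary outcome 2 describes load on coated curtains and cannot by itself support a conclusion about durability. That follows from the definition and needs no numerical assumption: any nonzero shared drift enters the treated-only trend in full. How often it would mislead depends on drift and correlation that the documents do not give. Under the assumed shared drifts of 0.05 to 0.15 log/week at SD 1 log, a pooled test of the treated slope would show a change with an intact coating in 10% to 97% of trials. The controlled contrast stays at about 5% if both arms drift equally on the log scale. The point should be corrected before any durability statement is made.

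**What to change.** - Keep the treated-only trend, labelled as description.
- Add the arm-by-week interaction: the change across the three weekly samples in the coated-minus-control difference in log10 CFU/m². Use a mixed model with phase and cubicle terms, a random curtain effect and preferably a curtain-by-visit effect.
- Estimate the interaction pooled over the three phases. Show phase-specific estimates without separate significance claims.
- Report the coated-minus-control difference with its 95% CI at each sampling week.
- Curtain installation, item 5, allows for replacement ("There was a backup pair of the curtain in case of need to change curtain due to spoilage"). Enter a curtain replaced during a phase as a new curtain with its own time since hanging.
- State that the contrast assumes equal log-scale drift in both arms when the coating is intact, and that a non-significant result does not show durability.
- Align the objective, the outcome definition and both analysis descriptions, or drop the durability wording.

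The cost is analysis time only, since control curtains were sampled on the same schedule. Study Status records data collection as completed in June 2018, so the contrast must be labelled post hoc. The other cost is precision: the larger SE and limited power shown above mean that the result may be inconclusive.

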### Basic information of previous field study in orthopedic ward

#### Assumptions:

1. The sample taken may have a higher standard deviation than the previous study. SD assumed to be 1log.
2. 0.21 log reduction on the total bacteria count on the bed partition curtains was assumed. This was based on the difference of the control and the treatment group in the previous study.

t tests - Means: Difference between two independent means (two groups)

Analysis: A priori: Compute required sample size

Input: Tail(s) = One  
 Effect size d = 0.2000000  
 α err prob = 0.05

	Power (1- $\beta$ err prob)	=	0.95
	Allocation ratio N2/N1	=	1
Output:	Noncentrality parameter $\delta$	=	3.2924155
	Critical t	=	1.6462631
	Df	=	1082
	Sample size group 1	=	542
	Sample size group 2	=	542
	Total sample size	=	1084
	Actual power	=	0.9500669

Hence a minimum of 1084 specimens were adequate for our study. To best fit the wards size and sampling schedule, we reckon a sample size of 1800 was best suited for our study.

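### Durability (primary outcome 2) has no criterion, and a week-by-week test within coated curtains cannot support it: non-significance does not show persistence, and background contamination is mixed with coating loss

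*Combined protocol and SAP*

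**What the plan says.** Primary Outcome Measure, item 2 (durability): "Change in bacterial load amongst treatment curtains is observed as a function of time during each phase". Each phase lasts four weeks. No hypothesis, minimum retained effect, margin or decision rule follows.

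Detailed Description, item [7], contains the only inference that mentions weeks: "ANOVA analysis allowed the comparison of different periods of study of phase wise as well as week wise", with "The significance of the statistical test is defined to have a P value <0.05". It does not name durability and is not limited to coated curtains.

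The Data Analysis section describes ANOVA differently: "ANOVA analysis allowed the comparison of different periods of study and the differences among wards". There is no week factor and no durability analysis there. The threshold is the same: "The significance of the statistical test was defined to have a P value <0.05".

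The sample size section covers only the coated-versus-control comparison of total bacteria count. Study Objectives 1(i) does list a comparison of coated with standard curtains on total count over time, but no test is attached to it.

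**The concern.** A durable coating is one whose effect does not fade, so the hoped-for pattern is no upward trend in the coated curtains. An ANOVA tests for a difference. With no estimate, bound or margin planned, the only output of that test that could be offered in support of durability is a P-value above 0.05, and few samples or noisy counts make that more likely.

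The restriction to coated curtains adds a second problem. The count on a coated curtain reflects both the coating and how much contamination reaches it. The sections on curtain installation and environmental sampling both expect curtains to become contaminated in use. A rise can therefore be ordinary build-up with the coating intact, and a flat profile can be a failing coating under falling exposure.

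At stake is one of two primary outcomes: a statement that the effect lasts, or that it fades, would have no error control in either direction.

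**Working it through.** **Inputs from the documents**
- Planning SD 1 log; effect 0.21 log in the text ("0.21 log reduction on the total bacteria count on the bed partition curtains was assumed"), 0.20 as the effect size entered (Assumptions).
- Previous study's SD in the treatment group: 0.544 log (Sample size calculation).
- 912 coated samples and three visits per curtain: 912/3 = 304 per visit, phases pooled.
- Samples per phase 480, 576 and 768 (work plan), half of them coated, three visits: 80, 96 and 128 coated samples per visit. Detailed Description prints 786 for the third phase, but its total of 1824 requires 768.

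**Assumptions not in the documents**
- The 0.2 log effect is lost linearly, so coated means rise by 0, 0.1 and 0.2 log over the three visits.
- Background contamination is flat.
- Swabs are independent.

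**Step 1: the plan's own figure.** One-sided t-test, "α err prob = 0.05", d = 0.20, 542 per group: noncentrality = 0.20 × √(542/2) = 3.2924, critical t = 1.6463, power 0.95007. The printed total of 1084 reproduces. No power is stated for durability.

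**Step 2: chance that a week ANOVA in coated curtains misses complete loss.** Noncentrality λ = n × Σ(mean deviation)² / SD². The deviations are −0.1, 0 and 0.1, so the sum of squares is 0.02. Power comes from the noncentral F with 2 and 3n − 3 degrees of freedom.

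| Coated samples per visit | λ, SD 1 | Missed | λ, SD 0.544 | Missed |
|---|---|---|---|---|
| 304 (pooled) | 6.08 | 41% | 20.52 | 1% |
| 80 (phase 1) | 1.60 | 81% | 5.40 | 47% |
| 96 (phase 2) | 1.92 | 78% | 6.48 | 38% |
| 128 (phase 3) | 2.56 | 72% | 8.64 | 25% |

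Pooled at SD 1, a loss of 0.21 log is missed 37% of the time. An abrupt loss of 0.2 log, after the first visit or only at the third, is missed 28% of the time.

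**Step 3: rising background (assumed), pooled, SD 1.**
- Background rises 0.2 log linearly and the coating is fully durable: the coated means are again 0, 0.1 and 0.2, so λ = 6.08 and the durable coating is flagged as changing 59% of the time.
- Background rises 0.1 log and the coating loses 0.2 log: means 0, 0.15 and 0.30, λ = 304 × 0.045 = 13.68, flagged 92% of the time.

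**Step 4: adding controls but still reading non-significance as durable.** For the arm-by-week test with flat controls, λ = 304 × 0.02 / 2 = 3.04. Power is 0.325, so complete loss is missed 68% of the time. Controls remove the confounding with background but do not make a non-significant result evidence of persistence.

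**Step 5: estimating the effect at the third visit.** SE of coated minus control = √(2/304) = 0.081 log. One-sided 5% power for a retained 0.2 log effect = Φ(0.2/0.081 − 1.645) = 79%. With an assumed within-visit curtain ICC of 0.1 and eight areas per curtain, the design effect is 1 + 7 × 0.1 = 1.7, the SE is 0.106 and power is 60%. A coating with no effect left passes 5% of the time by construction.

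**Step 6: change in effect from first to third visit.** SE = √(4/304) = 0.115 log, so the two-sided 95% half-width is 1.96 × 0.115 = 0.22 log.

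**The case against.** A reader might infer that the plan rests durability on the week-wise ANOVA and counts a non-significant result as a pass. The documents do not say this. The outcome is worded descriptively, Detailed Description does not link the ANOVA to durability or to coated curtains, and the Data Analysis section has no week factor. That part of the objection stands, so the error rates above are conditional on a reading that the investigators may never have intended.

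It is also fair that 41% is one scenario. It needs phases pooled, SD 1, linear loss between the first and third visits and flat background. Pooled at the previous study's SD, the miss rate is about 1%. Against that, the plan itself chose SD 1 because it expected more spread than before, and it words the outcome by phase, where the rates are 72–81% at SD 1 and still 25–47% at 0.544.

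Nor is false reassurance the established direction of error: step 3 shows that it can reverse.

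Finally, the 79% in step 5 should not be set against the 59% power in step 2 as a gain in efficiency. One is a one-sided single contrast, the other a two-degree-of-freedom test; a one-sided comparison of first and third visits within coated curtains has the same SE of 0.081. The gain lies in what is estimated.

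What survives all of this is that a primary outcome has no criterion and no linked analysis, and that the only candidate test cannot support the claim.

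**Conclusion.** The point holds in this form. Durability is assessed as change over time in coated curtains, without a criterion, and the only week-wise inference is a difference test not explicitly tied to it. Neither outcome of that test answers the question.

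If non-significance were taken as durability, the chance of missing loss of the whole 0.2 log effect runs from about 1% to 81%, depending on the SD and on whether phases are pooled, all under linear loss, flat background and independent swabs. Rising background can turn the error round. The range is wide, but the fault in the logic does not depend on any of these figures.

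The stronger statement, that a failed coating passes as durable about four times in ten, is not supported: it assumes a decision rule the documents do not contain and selects one scenario.

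**What to change.** Report the coated-minus-control difference in mean log10 count at each weekly visit with confidence intervals, using curtain means or a model with curtain as a random effect. Report the change in that difference from the first to the third visit with its interval.

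Conclude that the coating still has an effect at the third visit only if the one-sided 95% bound on that difference excludes zero. This shows some remaining effect, not a maintained one: at SE 0.081, a coating left with 0.1 log would pass 34% of the time. Make no claim that the effect is fully maintained unless the interval for the change excludes a stated loss. State that a non-significant week or arm-by-week test is not evidence of durability.

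Study Status gives data collection as complete in June 2018, so the analysis must be labelled post hoc.

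The cost is some wording and one table from data already collected. The downside is that the claim becomes harder to make: about 79% power for a retained 0.2 log effect with independent swabs at SD 1, and about 60% at an assumed ICC of 0.1. At SD 1 the interval for the change, about ±0.22 log, is wider than the planned effect, so a claim of full maintenance may be out of reach.
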